7.2.2 Anticipated enrollment by APS categories

Most patients enrolled according to the eligibility criteria of this study will have ARDS, pneumonia, and/or sepsis according to current diagnostic criteria for these syndromes at some point during the index hospitalization.³⁻⁸ Eligibility criteria for this study require participants to have evidence of acute cardiopulmonary organ dysfunction, operationalized as receiving vasopressors, new substantial oxygen therapy (at least 6 liters per minute of supplemental oxygen over baseline), or new respiratory support (high-flow nasal cannula, non-invasive ventilation, or invasive ventilation).

[figure not shown]
Figure 1 displays anticipated enrollment numbers by syndrome. Importantly, there is substantial overlap among ARDS, pneumonia, and sepsis, such that many enrolled patients will have more than one of these syndromes. The number of participants in each category cannot be anticipated perfectly. Throughout the enrollment period of the study, the APS Consortium Steering Committee will issue guidance to enrolling sites to help ensure the final cohort includes at least 1000 patients with ARDS, 2000 patients with pneumonia, and 2000 patients with sepsis.

Eligibility criteria for this study limit enrollment of patients with pneumonia to those on vasopressors or newly treated with ≥ 6 liters per minute of supplemental oxygen or respiratory support. Therefore, nearly all patients enrolled with pneumonia are expected to have a Sequential Organ Function Assessment (SOFA) score ≥ 2 via cardiovascular dysfunction (vasopressor use) or respiratory dysfunction (P:F ratio < 300),⁹ and therefore also meet the Sepsis-3 criteria for sepsis.⁸ The enrolled pneumonia cohort will include patients with pneumonia causing acute cardiovascular or respiratory organ dysfunction.

The most common cause of sepsis in this cohort is anticipated to be pneumonia. Patients with sepsis without pneumonia (non-pulmonary sepsis) meeting the eligibility criteria will also be enrolled. The enrolled sepsis cohort will include patients with sepsis causing acute cardiovascular or respiratory organ dysfunction, regardless of the etiology of sepsis. Patients who have suspected infection and a SOFA score ≥ 2 (a common operationalization of the Sepsis-3 definition) without acute cardiovascular or respiratory dysfunction will not be enrolled. Sepsis with a SOFA score ≥ 2 can occur without cardiovascular or respiratory dysfunction if organ dysfunction is present in the central nervous system (GCS ≤ 12), coagulation system (platelets $< 100,000$ /mcl), liver (serum total bilirubin ≥ 2.0 mg/dl), or kidneys (creatinine ≥ 2.0 mg/dl).

Patients with ARDS meeting study eligibility criteria will be enrolled regardless of whether the etiology of ARDS is pneumonia (anticipated to be most common), non-pulmonary sepsis (anticipated to be second most common), or an insult other than infection (anticipated to be least common).

Figure 1. Anticipated overlap of ARDS, pneumonia, and sepsis among participants enrolled in the APS Consortium cohort study. Displayed numbers are projections based on published cohorts and investigator experience; actual enrollment numbers may differ and will be followed closely throughout the recruitment period to ensure adequate numbers of patients with ARDS, pneumonia, and sepsis.

7.3 Definition of Enrollment Time Zero

The calendar day of the first study-specified biospecimen collection is defined as “Day 0.” The study schedule of events follows “study day” nomenclature, with enrollment day (the day of the first biospecimen collection) identified as Day 0. Study Day 1 is the calendar day following enrollment. Study Day -1 is the calendar day before enrollment. In some circumstances, consent for participation may be obtained after Day 0 (such as on Day 1) or prior to Day 0 (such as Day -1).

Time zero for enrollment is defined as the time of the first biospecimen collection for the study, regardless of the timing of hospital admission, consent, and development of ARDS, pneumonia, or sepsis. A patient is considered enrolled when the first study-specified biospecimen collection occurs. Time stamps will be collected for key events, such as hospital admission, meeting study eligibility criteria, and collection of biospecimens, so that analyses can evaluate the time between these events.

8. Study Procedures During Index Hospitalization

8.1 Data collection during index hospitalization

Data collection approaches within the APS Consortium are designed to optimize: (a) participant experience; (b) the scientific integrity of the Consortium-wide scientific aims; and (c) a robust and useable biobank for future research that is consistent with applicable regulations, guidance, and ethical norms.

8.1.1 Participant/surrogate interview

Attempts will be made to interview enrolled participants (or a surrogate) during the index hospitalization. The purpose of the interview (which may be performed with the participant's surrogate if the participant is unable to participate in the interview) is to obtain contact information (which has been demonstrated to improve cohort retention), to assess baseline health and health behaviors, to assess race/ethnicity and skin tone, to understand social drivers of disease at baseline, and to assess for preexisting comorbidities and frailty. Domains of data collection via interview include:

- Contact information of patient and family members
- Skin color (Monk skin tone scale)
- Self-assessment of overall health (5-point Likert scale from Health & Retirement Study)
- Smoking status (current/former/never; pack-years)
- Alcohol use (AUDIT-C)
- Health-related quality of life (EQ-5D-5L)
- Frailty (Clinical Frailty Scale)
- Functional Limitations (Katz ADL/Lawton IADL)
- Disability (WHODAS-12)
- Employment status (ICAP-Revised)
- Cognitive function (IQ-CODE)
- Social isolation (NHATS-6)
- Engagement with healthcare (National Health Interview and All of Us Surveys)
- Education (Health and Retirement Study)
- Housing instability (Council of State Governments)
- Current/former opioid misuse (ARDS Network Long Term Outcomes Study)

8.1.2 Medical record data abstraction

Medical record data abstraction, elements of which may be confirmed via patient/surrogate interview, may occur at varying times during the hospitalization based on operationalization at a given site. These data, whether extracted at the time of a given study visit or near or after hospital discharge, will be tied to

the schedule of events. Features of data abstraction will be extracted to correspond with the baseline visit as well as subsequent visits. Domains of data collection via medical record review include:

- Contact information of patient and family members, including home address and type of residence
- 9-digit zip code. This allows for linkage to other datasets to capture measures of social vulnerability (e.g., Social Vulnerability Index, Social Deprivation Index, Area Deprivation Index), as well as healthcare availability and rurality. Note: to avoid risk of re-identification of study subjects, zip code will be stripped from shared datasets; data on social vulnerability, healthcare availability, rurality, and other factors obtained by linkage to 9-digit zip code will be retained as categorical variables in shared datasets.
- Demographics
- Home medications
- Biometrics (height, weight)
- Language fluency
- Place of residence
- Chronic health conditions (including tobacco use, alcohol misuse, and opioid misuse)
- Health insurance status
- Prior hospitalizations
- Clinical laboratory results, medications, and vital signs, including SOFA score elements
- Therapies administered (including respiratory support therapies)
- Discharge disposition

8.1.3 Acute Respiratory Distress, Pneumonia, and Sepsis Syndrome Classification

Enrolled participants will be evaluated for ARDS, pneumonia, and sepsis utilizing detailed, investigator driven review and application of published and accepted clinical criteria for each syndrome. To evaluate for ARDS, pneumonia, and sepsis, investigators will evaluate data and the clinical record for each participant for Study Day -2 through Day 7 while the patient is hospitalized (the phenotyping observation window). Individual criteria for each syndrome will be collected and recorded separately allowing for patients to be classified as ARDS, Sepsis, and/or Pneumonia using multiple published criteria (e.g., for sepsis using both “sepsis-2” and “sepsis-3” criteria). These data will then be used to code variables in our dataset that classify patients according to syndrome definitions. Standard operating procedures will be provided to each site to ensure accuracy and consistency of syndrome adjudication.

ARDS will be identified based on the Berlin Definition with the additional modifications proposed in the New Global Definition of ARDS.^{3,4} Trained physician investigators will determine the presence of potential precipitating factors for ARDS (e.g., sepsis, aspiration, pancreatitis). Chest radiographs and chest computed tomography scans conducted for clinical purposes during the observation window will be reviewed by trained physician investigators for bilateral infiltrates consistent with ARDS. The type of chest imaging, time and date of imaging acquisition, and bilateral infiltrates present, absent, or equivocal will be recorded in case report forms. The presence or absence of pleural effusions will also be recorded. Arterial blood gas (ABG) values drawn for clinical purposes and corresponding fraction inspired oxygen percentage (FiO₂) will also be recorded in case report forms. If an ABG is unavailable on a given day,

SpO₂ and corresponding FiO₂ will be recorded to calculate the S/F ratio. Invasive and non-invasive oxygenation and ventilation parameters will also be extracted from the medical record. We will apply strict physiologic criteria in ARDS definitions to determine the presence or absence of ARDS daily, timing when ARDS criteria are met, and the severity of ARDS based the level of hypoxemia (P:F and S:F ratios).

Participants will be assessed for the presence of pneumonia based on radiographic, clinical, and laboratory criteria, including those published by CDC and the Infectious Disease Society of America/American Thoracic Society.^{5,6} Chest imaging conducted for clinical purposes during the phenotyping observation window will be reviewed by trained physician investigators for new/persistent/progressive infiltrates, consolidation, or cavitation consistent with a pneumonia event. Clinical signs and symptoms potentially indicating a respiratory infection will be identified, including vital signs, laboratory results, and clinical status. Assessment of clinical status will include: 1) new onset purulent sputum or change in character of sputum, increasing respiratory secretions, or increasing suctioning requirements, 2) new onset or worsening cough, dyspnea, or tachypnea, 3) rales or bronchial breath sounds, and 4) worsening gas exchange. These data will form the core dataset for classifying the presence and absence of pneumonia.

Sepsis will be identified based on the Sepsis-2 and Sepsis-3 definitions of sepsis, severe sepsis and septic shock.^{7,8} Trained physician investigators will review the medical record to determine if an infection is confirmed, suspected, not suspected, or unknown daily for the observation window. The presence of positive culture will not be required to identify the confirmed or suspected presence of an infection; however, positive cultures can be used to help determine the presence of sepsis. Suspected sources of infection will be adjudicated by the physician investigators. The physiology of sepsis and septic shock will be classified based on the change in Sequential Organ Function Assessment (SOFA) scores, the presence or absence of the systemic inflammatory response (SIRS) criteria, the presence or absence of vasopressors, and values for lactate. These data will be used to facilitate sepsis classification by the investigator adjudicators.

8.2. Biospecimen collection during index hospitalization

Aliquots of biospecimens collected on this research protocol may be sent for clinical laboratory testing if such testing is judged to be of potential benefit to the patient. Clinical laboratory testing is optional and may be completed at the discretion of the local site team. If clinical laboratory testing is completed, results may be delivered to clinicians caring for the patient according to local practice patterns.

8.2.1 Blood specimen collection during index hospitalization

During the index hospitalization, blood will be collected from patients at multiple timepoints, collected in EDTA or sodium citrate tubes (for protein or metabolite measurements), PAXgene tubes (for nucleic acids), CPT tubes (for peripheral blood mononuclear cells), and sodium heparin tubes (for whole blood CyTOF and flow cytometry). Blood will be collected at the timepoints indicated in the schedule of events for biospecimen collection (Section 10). Participants known to be pregnant will only have blood collected

during the index hospitalization on Day 0 and Day 2, ensuring <50 ml of blood volume collected in any 8-week period and ≤ 2 blood draws in any 1-week period for research purposes, which is considered to be no greater than minimal risk in guidance from the Office Human Research Protections (OHRP) [<https://www.hhs.gov/ohrp/regulations-and-policy/guidance/categories-of-research-expedited-review-procedure-1998/index.html>].

8.2.2 Respiratory specimen collection during index hospitalization

During the index hospitalization, the following respiratory specimens will be collected: 1) nasal swabs to facilitate both microbiome profiling and pathogen detection, 2) oral swabs, 3) tracheal aspirate (TA) from patients receiving invasive mechanical ventilation, 4) heat moisture exchanger (HME) filter fluid from patients receiving invasive mechanical ventilation, 5) non-bronchoscopic bronchoalveolar lavage (NBBAL) fluid among a subset of patients receiving invasive mechanical ventilation.

Description of the NBBAL procedure in this study:

The NBBAL procedure will be completed in a subset of participants undergoing invasive mechanical ventilation after a safety screen for the procedure (see below) and consent is obtained. The NBBAL will be performed as soon as possible (and no later than 96 hours) after initiation of invasive mechanical ventilation. The NBBAL procedure will entail a catheter being inserted into the endotracheal tube and the catheter tip being wedged into a distal airway. Serial aliquots of sterile saline are instilled and aspirated with gentle suction (maximum volume instilled, 120ml). The aspirated fluid will be collected and processed as a biospecimen for the study.

Safety Screen for NBBAL in this study:

Participants meeting any of the following criteria will not undergo NBBAL for research purposes in this study:

1. Known pregnancy
2. $FiO_2 \geq 0.80$.
3. FiO_2 increased by > 0.1 in the prior hour.
4. $PEEP \geq 12$ cm H₂O.
5. $PEEP$ increased by > 2 cm H₂O in the prior hour.
6. Intracranial pressure > 15 or known labile intracranial pressure.
7. Open external ventricular drain (EVD).
8. Known pneumothorax.
9. Uncontrolled shock or rapidly escalating vasopressor requirements.
10. Unstable dysrhythmia.
11. Scheduled bronchoscopy.
12. Current therapeutic anticoagulation.
13. Known $INR > 2.0$.
14. Platelets $< 50,000$ /mcL.
15. Frank hemoptysis.
16. Partial lung resection or pneumonectomy.
17. Known pulmonary hypertension with pulmonary artery systolic pressure (PASP) > 55 cm H₂O.
18. Expected extubation attempt in the next 6 hours.
19. Clinical provider or site investigator judgement that procedure would not be safe.

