Tracheal aspirate fluid collection	Bleeding, localized pain, drop in oxygen levels (hypoxemia), and dislodgement of the tracheal tube. A drop in oxygen levels from tracheal aspirate collection is very unlikely to cause patient harm.	Only study or clinical personnel trained in the collection of tracheal aspirate fluid will collect this specimen. Tracheal suctioning is a routine clinical procedure and tracheal aspirates for this protocol will be done at times that tracheal aspirates are being collected as part of clinical care, whenever possible.
NBBAL procedure	Bleeding, localized pain, dislodgement of the tracheal	Only study or clinical personnel trained in the NBBAL procedure will complete this procedure for the study. NBBAL

Study procedure	Potential risks	Study methods to minimize risks
	tube, and drop in oxygen levels (hypoxemia), which if severe and uncorrected, can lead to organ injury and death. Serious injury from a NBBAL is rare (<1%). ²³	is a common clinical procedure in some hospitals. Only patients who are intubated will undergo the NBBAL procedure. Only patients who pass a pre-procedural safety screen under the supervision of the site investigator will undergo a NBBAL. Hypoxemia temporally related to a study NBBAL procedure will be collected as an AESI and reported to the sIRB and OSMB.
Long-term outcome surveys (via phone, SMS, or email)	No plausible physical risks. Participants might experience embarrassment or emotional discomfort.	Participants do not have to answer any questions that make them feel too uncomfortable. An on-call mental health specialist will be available to talk with patients that have severe emotional stress or suicidal thoughts.
Short physical performance battery (SPPB) [at in-person LTO visits]	SPPB assesses lower extremity functioning. It includes a balance test, a timed 4-meter walk test, and chair stand test. There is a small risk of falling. Activities may increase heart rate.	The testing will be performed by trained study staff. Movements are completed in a standard order, starting with easier movements. Participants will be able to skip any movement that they cannot do or feel would be unsafe to try.
CNS-Vital Signs [at in-person visits]	CNS vital signs is a computer based cognitive assessment. Participants might experience embarrassment or emotional discomfort from not being able to answer some questions.	Participants do not have to answer any questions that make them feel too uncomfortable.

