16.3.5 Aim 3 Study Procedures

HME filter fluid studies:

After passing a safety screen to rule out severe hypoxemia ($FiO_2 > 80\%$) or high PEEP (>15 cm H₂O), HME fluid will be collected on days 0, 2, 4, 6 and 14 if patient is mechanically ventilated by placing a fresh Airlife HME filter in the ventilator circuit for 4 hours. Patients who are intubated prior to enrollment will have the first (day 0) sample collected on the day of enrollment. The Airlife HME filter is optimal for these studies, with a small dead space volume and a reliable HME fluid yield of ~1-2 ml after a 4-hour dwell time.⁵ At study sites where heated ventilator circuits are routinely used, the heated circuit will be removed or turned off for the 4-hour HME dwell time. Once removed, HME filters will be centrifuged to collect exhaled breath condensate which will be frozen in small aliquots.

A panel of protein biomarkers representing key facets of lung pathology during acute respiratory failure will be measured in duplicate in HME samples including IL-6, IL-8, TNFR1, MCP1, RAGE, SP-D, Angiopoietin-2, ICAM-1, procollagen peptide-3, protein C, PAI-1 and total protein.

NBBAL studies:

All patients that are initiated on mechanical ventilation will be considered for NBBAL. Ideally, NBBAL will be performed within 24 hours of initiation of mechanical ventilation. However, we recognize that this might not be feasible for all participants. Therefore, NBBAL may be performed as late as 96-hours after initiation of mechanical ventilation. Safety criteria for NBBAL include $FiO_2 \leq 75\%$, $PEEP < 15$, $INR \leq 3.0$, and platelets $> 50,000 / \text{ul}$. All must be met at the time of the procedure. Prior to performing NBBAL, the patient is placed on 100% FiO_2 for 10 minutes. BAL is performed using a flexible 16 gauge catheter that is gently advanced through the endotracheal tube to “wedge” the distal tip of the catheter. Serial aliquots of saline are instilled into the catheter and then aspirated. The maximum instillation volume is 120 ml.

Aspirated BAL fluid will be pooled and placed in a sterile collection container and kept on ice until processing. BAL fluid will be run through a 70 micron strainer to remove mucus and debris. Fluid will be centrifuged to pellet cells. Cell-free fluid is gently aspirated and aliquoted for banking. Cells will be washed once, and then preserved for RNA sequencing studies.

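### The pulmonary artery pressure limit in the NBBAL safety screen is printed in cm H2O, so the limit as written is about 40 mmHg rather than the 55 mmHg probably intended (minor)

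*Protocol*

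**What the plan says.** Protocol section 8.2.2 sets a 19-item safety screen for research NBBAL. Any single item is enough to rule the procedure out: "Participants meeting any of the following criteria will not undergo NBBAL for research purposes in this study". Item 17 is "Known pulmonary hypertension with pulmonary artery systolic pressure (PASP) > 55 cm" H2O, so the unit is printed in full. Items 4 and 5 of the list give PEEP limits in the same unit. Item 6, the other pressure in the list that is not an airway pressure, has no unit at all: "Intracranial pressure > 15 or known labile intracranial pressure".

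No other section restates the PASP limit. Section 16.3.5 (Aim 3 Study Procedures) has a second, shorter list. It opens with "Safety criteria for NBBAL include", covers FiO2, PEEP, INR and platelets, and adds "All must be met at the time of the procedure". It has no PASP item.

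Two further provisions bear on how much the item matters. Item 19 of the screen bars the procedure on "Clinical provider or site investigator judgement that procedure would not be safe". Table 13 in section 13.1 says: "Only patients who pass a pre-procedural safety screen under the supervision of the site investigator will undergo a NBBAL".

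**The concern.** PASP is a vascular pressure, and cm H2O is an airway-pressure unit. The PEEP items stand in the same list, so the likeliest explanation is that their unit was carried over and that 55 mmHg was meant. The text does not say this, and read literally it sets a clearly different limit.

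The item is unsatisfactory whichever limit was meant:

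- If 55 mmHg was intended, the printed unit is wrong. A site that follows the text exactly excludes patients the sponsor wanted to sample.
- If 55 cm H2O was intended, the limit is in a unit that does not match the chart. A site that compares the numbers directly lavages patients the text bars.

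At stake is one go/no-go threshold for an invasive procedure done for research. Table 13 lists hypoxemia among its risks, with possible organ injury and death if it is severe and uncorrected, and relies on the pre-procedural screen as a protection. The protocol rates serious injury as rare (below 1%).

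**Working it through.** There is no power, sample size or error rate to reproduce here. The check is a unit conversion followed by a classification under each reading.

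**Inputs**

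- Limit: PASP > 55 cm H2O (section 8.2.2, item 17).
- Direction: meeting any one item bars NBBAL (section 8.2.2).
- Conversion: 1 cm H2O = 98.0665 Pa and 1 mmHg = 133.322 Pa, so 1 cm H2O = 98.0665 / 133.322 = 0.73556 mmHg.
- Assumption: PASP is charted in mmHg.

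**The limit under each reading**

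- As printed: 55 × 0.73556 = 40.5 mmHg.
- With 55 read as mmHg: 55 / 0.73556 = 74.8 cm H2O.
- Ratio: 55 / 40.46 = 1.36, so the second limit is about 36% higher than the printed one.

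**Classification of charted values**

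| PASP (mmHg) | Equivalent (cm H2O) | As printed (> 55 cm H2O) | 55 read as mmHg |
|---|---|---|---|
| 40 | 40 / 0.73556 = 54.4 | passes | passes |
| 41 | 41 / 0.73556 = 55.7 | barred | passes |
| 50 | 50 / 0.73556 = 68.0 | barred | passes |
| 55 | 55 / 0.73556 = 74.8 | barred | passes |
| 56 | 56 / 0.73556 = 76.1 | barred | barred |

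In whole mmHg the two readings disagree only from 41 to 55. At 40 and below, and at 56 and above, they agree.

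**Can the protocol settle the unit?** It cannot. Item 6 has no unit and so gives no guide. The list in section 16.3.5 has no PASP item, so it neither supports nor contradicts either reading. Elsewhere in the protocol cm H2O is used for PEEP, including the PEEP limit for HME filter sampling in section 16.3.5. That makes a carry-over plausible but does not prove it.

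**How many patients?** About 700 NBBALs are anticipated (section 16.3.8 and Table 9). The protocol gives no figure for how many ventilated participants have known pulmonary hypertension with a recorded PASP, still less for how many fall between 41 and 55 mmHg. The number affected cannot be derived and may be very small.

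**The case against.** The strongest reply is that this is a copy-editing matter. Item 17 states a number, a unit and a direction, and nothing else in the protocol contradicts it. That mmHg was intended is an inference. Nor is harm shown. If 55 mmHg was meant, a site comparing 55 with the chart applies exactly the intended limit, and a site that converts applies a stricter one, which costs a few specimens but errs toward safety. A patient is exposed beyond the intended limit only if 40.5 mmHg was truly meant and sites did not convert, which is the less likely case. Safeguards also exist: clinician or investigator judgement under item 19, site-investigator supervision of the screen, hypoxemia after NBBAL as an adverse event of special interest (section 14.2.2), and safety monitoring by the OSMB (section 14.3). Any operational screening form may already use mmHg.

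Much of this stands. The intended limit is not proved, divergence between sites is not shown, no harm is demonstrated, and the form is not part of the protocol. The printed pressure is also definite, so a departure from it can be identified.

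These points bear on severity and leave the printed limit as it is. A threshold in an operative safety screen should be the one the sponsor meant, in a unit staff can compare with the chart. Item 19 is a discretionary stop. It can keep a patient out, but it cannot bring back one whom the literal limit wrongly excluded. A form in mmHg would leave the form and the protocol stating different limits.

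**Conclusion.** The point holds and is minor. The printed limit is 40.5 mmHg, the probable intent is 55 mmHg, and a known PASP of 41 to 55 mmHg is classified differently under the two readings. The conversion is exact. The rest depends on the assumption that PASP is charted in mmHg, and the view that 55 mmHg was intended is a likely inference that only the sponsor can confirm.

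The item reaches only ventilated participants with known pulmonary hypertension and an available PASP, and the number in the band is unknown. Every site may already read 55 as mmHg and so apply one common limit. No sample size, endpoint or analysis is affected.

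**What to change.** Ask the sponsor which pressure was meant, then restate item 17 in mmHg: above 55 mmHg if that was intended (the likely case), or above 40 mmHg if the literal 55 cm H2O was intended. Bring any NBBAL screening form into line with the corrected item.

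The cost is one line in section 8.2.2 and the matching line of the form. It changes no data collection or analysis and can go into the next amendment.
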